5. I agree to maintain adequate and accurate records in accordance with CHR policies, Federal, state and local laws and regulations.

UCSF Principal Investigator / Study Chair

Printed Name

Signature

Date

Participating Site(s)

Telephone:
E-mail:

Telephone:
E-mail:

Telephone:
E-mail:

Principal Investigator

Site

Printed Name

Signature

Date

Abstract

Title	A Pilot Trial of Using Pre-Transplant Risk Stratification and Prophylactic Defibrotide to Prevent Serious Thrombotic Microangiopathy in High-Risk Hematopoietic Stem Cell Transplant Patients
Patient population	Pediatric patients age 0-30 years receiving autologous or allogeneic HSCT meeting TMA high risk criteria.
Rationale for Study	TMA is a common complication in the stem cell transplant population. Certain populations within the HSCT population are at a higher risk than others. Defibrotide is an endothelial stabilizing agent which may prevent the endothelial damage that triggers TMA in HSCT patients. The feasibility, safety, and efficacy of defibrotide prophylaxis in a pediatric transplant population is unknown.
Primary Objective	To determine the feasibility and safety of defibrotide in children receiving HSCT.
Secondary Objectives	To determine the efficacy of defibrotide prophylaxis in preventing severe TMA in pediatric patients receiving HSCT.
Study Design	Single arm non-randomized Phase II safety and feasibility trial of un-blinded defibrotide prophylaxis.
Number of patients	25
Duration of Therapy	Patients may continue treatment for 28-35 days from time of study drug initiation.
Duration of Follow up	Follow up for 6 months post-HSCT per HSCT standard of care.
Duration of study	The study will reach completion 30 months from the time the study opens to accrual.
Study Drugs	Defibrotide 6.25mg/kg IV Q6h for 28-35 days.
Safety Assessments	Weekly inpatient assessments of administration feasibility, hypersensitivity reaction, and bleeding while defibrotide is administered. This includes all HSCT SOC evaluations including routine clinical evaluations and laboratory assessments.
Efficacy Assessments	Efficacy will be based on overall incidence of TMA as well as incidence of severe TMA within 6 months post-HSCT, as defined in the protocol.

Unique Aspects of this Study	This is the first study to evaluate safety and efficacy of defibrotide in pediatric patients for prevention of severe TMA.
------------------------------	--

List of Abbreviations

AE	adverse event
ALP	alkaline phosphatase
ALT	alanine aminotransferase
ANC	absolute neutrophil count
ANG-2	angiopoietin 2
AST	aspartate aminotransferase
ATC	Anatomical Therapeutic Chemical (Classification System)
AUC	area under the curve
BCH-SF	Benioff Children's Hospital- San Francisco
BMT	bone marrow transplant
BUN	blood urea nitrogen
CBC	complete blood cell (count)
CH50	complement activity
CHR	Committee on Human Research (UCSF IRB)
CR	complete response
CRC	Clinical Research Coordinator
CRF	case report form
CSF	cerebral spinal fluid
CT	computerized tomography
CTCEA	Common Terminology Criteria for Adverse Events
CTEP	Cancer Therapy Evaluation Program
CTMS	Clinical Trial Management System
DFS	disease-free survival
DLT	dose limiting toxicity
DSMP	Data and Safety Monitoring Plan
FCBP	female of childbearing potential
FDA	Food and Drug Administration
GCP	Good Clinical Practice
HBV	hepatitis B virus
HCT	hematocrit
HSCT	hematopoietic stem cell transplant
HCV	hepatitis C virus
HGB	hemoglobin
HIV	human immunodeficiency virus

List of Abbreviations

ICH	International Conference on Harmonization
IND	investigational new drug application
IP	investigational product
IRB	Institutional Review Board
IV	intravenous
LDH	lactate dehydrogenase
LFT	liver function test
MedDRA	Medical Dictionary for Regulatory Activities
MRI	magnetic resonance imaging
MTD	maximum tolerated dose
NCI	National Cancer Institute
ORR	overall response rate
PAI-1	plasminogen activator inhibitor – 1
PD	disease progression
PK	pharmacokinetics
PO	per os (by mouth, orally)
PR	partial response
PRES	posterior reversible encephalopathy syndrome
PRC	Protocol Review Committee (UCSF)
PT	prothrombin time
PTT	partial thromboplastin time
QOL	Quality of Life
RBC	red blood cell (count)
SAE	serious adverse event
SD	stable disease
SD	standard deviation
SGOT	serum glutamic oxaloacetic transaminase
SGPT	serum glutamic pyruvic transaminase
ST2	suppression of tumorigenicity
TBI	total body irradiation
TMA	thrombotic microangiopathy
TRM	treatment related mortality
ULN	upper limit of normal
WBC	white blood cell (count)

Table of Contents

Protocol Signature Page	1
List of Abbreviations	4
Table of Contents	6
1 Introduction	9
1.1 Background on Indication	9
1.2 Background on the Compounds	10
1.3 Rationale for the Proposed Study	10
1.4 Correlative Studies	11
2 Objectives of the Study	11
2.1 Primary	11
2.2 Secondary	11
2.3 Exploratory Objectives, Other Assessments	12
2.4 Endpoints	12
2.4.1 Primary Endpoints	12
2.4.2 Secondary Endpoints	12

1.1 Background on Indication

Hematopoietic stem cell transplant (HSCT) is associated with an appreciable degree of transplant-related (i.e. toxic) mortality (TRM). The incidence of TRM at 1-year post-HSCT ranges from 5-15% depending upon the stem cell source utilized (Wingard, J Clin Oncol 2011). The UCSF BCH-SF BMT program has reviewed all cases of non-relapse related death from 2012-2015 and identified a complication of endothelial injury known as transplant associated thrombotic microangiopathy (TMA) as the most common cause of TRM in our patient population.

TMA is a multi-system disease in which widespread endothelial injury leads to microangiopathic hemolytic anemia, intravascular platelet activation and formation of thrombi within the microcirculation. The endothelial injury then promotes the complement cascade leading to additional injury to the endothelium further propagating the disorder.

TMA predominantly occurs in the kidneys but can affect the liver, lungs, intestines and brain. The risk factors for the development of TMA include myeloablative and reduced intensity conditioning regimens, calcineurin inhibitors (tacrolimus, cyclosporine), mTOR inhibitors (sirolimus), and infections. Additional risk factors include mismatched donors, ABO mismatch, and non-Caucasian patients. When genetic testing was performed looking at seventeen genes involved in the pathogenesis of other thrombotic microangiopathies, non-Caucasian patients with TMA were found to have more genetic variations when compared Caucasian patients (Jodele, Blood 2016).

Diagnosis of TMA can be difficult as systemic signs and symptoms of TMA are often similar to other common transplant complications, such as medication induced hypertension and cytopenias. Unlike in thrombocytopenic purpura, patients with TMA have normal ADAMTS13 activity. A renal biopsy would be useful in diagnosis however is often not possible given the risk factors of the procedure in a transplant patient.

The reported prevalence of TMA is varied likely due to diagnostic uncertainty and center expertise, but large retrospective studies have reported it as 10-39%, with the majority of cases occurring in the first 100 days after transplant. Of the patients who develop TMA, approximately half of them will develop severe disease. Outcomes are poor with a reported 30-50% mortality rate and as high as 80% in patients with severe disease. Furthermore, survivors of TMA may have significant morbidity (e.g. renal failure and need for long-term dialysis, heart failure, and significantly prolonged hospital admission).

There is no gold standard of treatment for TMA. Supportive care including renal support, discontinuation of calcineurin inhibitors and treatment of infections. Treatment options include plasma exchange, complement cascade blockade, and defibrotide. Early treatment is crucial to decrease morbidity and mortality.

Interestingly, our most severe cases of TMA have occurred in patients NOT receiving calcineurin inhibitors or sirolimus. Despite the early recognition and treatment of TMA, we have continued to see poor outcomes treating with complement blockade alone. This suggests that complement activation may trigger a complex cascade of parallel inflammatory mediators that lead to end organ damage independent of the complement pathway. Therefore, our goal is to prevent TMA whenever possible via augmentation of endothelial repair.

1.2 Background on the Compounds

Refer to the Investigator's Brochure/approved labeling for detailed background information on defibrotide.

1.3 Rationale for the Proposed Study

Upon retrospective review of our cases of TMA and the medical literature, we are now classifying patients as either standard-risk for the development of TMA, or high-risk, based on the following clinical criteria:

1. Patients undergoing tandem autologous transplant with thiotepa in one or more of the conditioning regimens.

OR:

2. Patients with at least 3 of the following characteristics:
 - a) >10 years of age
 - b) Non-Caucasian race/ Hispanic ethnicity
 - c) Undergoing haploidentical transplant
 - d) Minor ABO Mismatch

Using these criteria, we retrospectively reviewed 160 transplants performed from 1/1/13 to 9/30/16. There were 13 cases of TMA total (8.1%), with 7 cases (4.4%) deemed severe by the onset of renal failure, development of pericardial effusion, and/or death. In the 138 standard-risk patients, there were 6 total cases of TMA, but only 1 was severe (0.7%). Conversely, in the 22 high-risk patients there were 7 total TMA cases, 6 of which were severe (27.3%). Most cases showed evidence of evolving TMA before Day +100 post-HCT, and some cases of TMA were evident within a week following HCT.

Several groups have demonstrated that the onset of endothelial injury and clinical TMA typically begins within 4-6 weeks following HCT (Jodele Blood Rev 2015, Obut BMT 2016). Therefore, the hypothesis is that in high-risk patients the administration of certain combinations of high-dose conditioning agents (radiation and/or chemotherapy) and/or post-HSCT inflammatory events initiate the complement pathway to aberrantly attack the endothelium. Although the current standard treatment for post-transplant microangiopathic processes involves targeting inflammatory mediators with complement blockade and plasmapheresis, these therapies do not address the prevention or treatment of the initial pathologic trigger, namely, endothelial damage.

Defibrotide is an anticoagulant and fibrinolytic agent that has been shown to be an effective treatment in other endothelial disorders such as hepatic veno-occlusive disease (Richardson Blood 2002). It is a polydeoxyribonucleotide salt that blocks plasminogen activator inhibitor-1 (PAI-1) and attenuates the effect of tumor necrosis factor. It also increases prostaglandin E2 and prostacyclin levels which alters the platelet activity adhesion and aggregation and relaxes the smooth muscle of blood vessel walls. All of this likely protects the endothelium from damage. Yeates et al have shown that patients with TMA who were treated with defibrotide had a 77% response rate. (Yeates et al, Bone Marrow Transplantation, 2017).

The use of defibrotide in the context of VOD treatment and prevention has been studied extensively. A landmark report showed that defibrotide given to children during stem cell

transplant conditioning is safe and effective in the prevention of veno-occlusive disease and, incidentally, acute graft-versus-host disease (Corbacioglu, Lancet 2012). However, there has not been a prospective study to show that such prophylaxis is effective in the prevention of TMA.

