8.1 Study Endpoints

- Open label non-randomized un-blinded study to determine feasibility, safety, and efficacy.
- Feasibility endpoints;
 - Incidence of discontinuation of defibrotide. Study will be suspended if defibrotide is not tolerated as outlined below:

N (accrued)	0-6	7-12	13-18	19-24
Evaluate if discontinued in this many or more patients:	5	8	10	12

- Safety endpoints
 - Incidence of reportable SAE's (possibly drug-related and severe or unexpected). Study will be suspended if reportable AE's

N (accrued)	0-6	7-12	13-18	19-24
Evaluate if drug-related SAE's occur in this many or more patients:	4	7	10	12

- Incidence of TMA
 - Historical incidence: 7 of 22 (31.8%). With N=24, study will have 80% power to detect a statistically significant difference if incidence in this treated cohort is 8% or less.
 - Study will be re-evaluated if 2 patients develop TMA as this will render the secondary endpoint futile. May continue enrollment to determine feasibility and safety or expand the patient cohort.
- Incidence of Severe TMA
 - Historical incidence: 6 of 22 (27.3%). With N=24, study will have 70% power to detect a statistically significant difference if incidence in this treated cohort is 4% or less.
 - Study will be re-evaluated if 1 patient develops severe TMA as this will render the secondary endpoint futile. May continue enrollment to determine feasibility and safety or expand the patient cohort.

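### The 31.8% and 27.3% historical TMA rates are unvalidated figures from 22 patients, picked out by criteria drawn partly from the centre's own cases; other things equal they are probably too high, and the comparison should carry that uncertainty

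*Combined protocol and SAP*

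**What the plan says.** Section 1.3 gives the order of events. The risk classification was adopted "Upon retrospective review of our cases of TMA and the medical literature". It has two routes: tandem autologous transplant with thiotepa, or at least three of four features (age over 10, non-Caucasian race or Hispanic ethnicity, haploidentical transplant, minor ABO mismatch). The section continues: "Using these criteria, we retrospectively reviewed 160 transplants performed from 1/1/13 to 9/30/16". The result is given as "in the 22 high-risk patients there were 7 total TMA cases, 6 of which were severe (27.3" per cent); the remaining 138 patients had 6 TMA cases, 1 of them severe.

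Section 1.1 adds that the centre's transplant programme "has reviewed all cases of non-relapse related death from 2012-2015 and identified" TMA as the commonest cause of transplant-related death.

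Section 8.1 carries the figures forward as the comparator ("Historical incidence: 7 of 22 (31.8" per cent, and 6 of 22 for severe TMA) and attaches power statements at N=24. Section 8.2.1 uses 28% for severe TMA and states 92% power against 4%, with a minimum N of 19 for 80% power. Section 8.4.3 compares trial incidence with historical controls but names no test and no rate. Section 2.2 sets the trial's TMA window at the first 6 months after transplant. Section 1.3 gives no window for the historical cases and says only that most were evolving before Day +100.

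**The concern.** When a classification is shaped by looking at cases and its event rate is then read from a series containing those cases, the rate tends to be too high. The choice of features and cut-offs favours whatever captured the known cases. New patients meeting the same rule would, other things equal, have a lower rate even if untreated.

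Two features of the rule suggest that the centre's cases had a real part in it. Thiotepa tandem transplant and age over 10 are not among the risk factors listed in section 1.1. Calcineurin inhibitors, sirolimus and infection are listed there but are absent from the rule, which fits the remark in the same section that the centre's most severe cases were not receiving calcineurin inhibitors or sirolimus.

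The efficacy objective in section 2.2 depends on this benchmark. There is no concurrent control, so an inflated historical rate and a drug effect would look the same in the data.

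**Working it through.** **Inputs.** Historical counts 7/22 and 6/22 (high risk), 6/138 and 1/138 (standard risk), from section 1.3. N=24, alpha 5%, 28% versus 4%, stated power 92% and minimum N 19, from section 8.2.1. The plan names no test and does not say whether alpha is one- or two-sided.

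**Step 1: what the plan's power figure assumes.** One-sample normal approximation, two-sided 5%:

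power = Φ[(|p0 − p1|√n − 1.96√(p0(1−p0))) / √(p1(1−p1))]

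With p0=0.28, p1=0.04, n=24: (0.24×4.899 − 1.96×0.449)/0.196 = 1.51, so power is 93.4%. At n=18 it is 76.0% and at n=19 it is 80.2%, so the minimum N is 19, as stated. The exact binomial test (reject if 2 or fewer of 24) has one-sided alpha 1.96% and power 93.1%. Both are within 2 points of the stated 92%.

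A two-sample test with 22 controls gives only 61.7% (two-sided) or 73.3% (one-sided) for the same rates. Section 8.2.1 therefore treats the 22-patient rate as a known constant. Section 8.1's 70% for 27.3% versus 4% is close to a one-sided two-sample calculation (71.6%), so the two sections appear to rest on different tests.

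**Step 2: sampling error of the benchmark.** Exact (Clopper-Pearson) 95% intervals:

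- 7/22 = 31.8%: 13.9% to 54.9%
- 6/22 = 27.3%: 10.7% to 50.2%

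These make no allowance for the way the criteria were chosen.

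**Step 3: results that would count as a benefit.**

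- All TMA, two-sided Fisher test against 7/22: 1/24 gives p=0.020 and 2/24 gives p=0.066. Success is 0-1 of 24.
- Severe TMA, exact test against a fixed 28%: P(X≤2)=0.0196 and P(X≤3)=0.0645. Success is 0-2 of 24.
- Severe TMA, two-sided Fisher test against 6/22: 1/24 gives p=0.043 and 2/24 gives p=0.128. Success shrinks to 0-1 of 24.

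**Step 4: chance of such a result with no drug effect.** X ~ Binomial(24, p), where p is the assumed true untreated rate of the endpoint in question.

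| Assumed true rate | P(X≤1) | P(X≤2) |
|---|---|---|
| 31.8% | 0.1% | 0.7% |
| 28% | 0.4% | 2.0% |
| 25% | 0.9% | 4.0% |
| 20% | 3.3% | 11.5% |
| 15% | 10.6% | 28.0% |

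The P(X≤1) column applies to all TMA and to severe TMA under the two-sample test. The P(X≤2) column applies to severe TMA against the fixed 28%. The rates 15%, 20% and 25% are assumptions; all three lie inside both intervals from step 2.

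**Step 5: do the criteria carry real information?** Fisher's test of high versus standard risk gives p=0.0004 for TMA (7/22 against 6/138) and p=0.00002 for severe TMA (6/22 against 1/138). Enrichment this strong is unlikely to be selection alone. The question is how large the high-risk rate is, not whether it is raised.

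**The case against.** **Overlap is not stated.** Section 1.3 does not date the cases behind the criteria, and section 1.1 does not say that the 2012-2015 death review produced them. This stands: overlap is an inference. It is a strong one, because the same centre is involved, the years 2013-2015 are shared, and no other case set is mentioned.

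**The literature also contributed.** Section 1.3 says so, and section 1.1 lists mismatched donors, ABO mismatch and non-Caucasian patients, which broadly match three of the four scored features. This stands and reduces the likely inflation, but does not remove it.

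**A reader might take the overall rate, 13/160 = 8.1%, as the floor to which new patients would regress.** The documents do not support that. It would mean that the criteria carry no risk information, against step 5. Nor is 31.8% a ceiling, since the interval reaches 54.9%.

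**A reader might also conclude that a new cohort must fall below the benchmark.** That holds only with all else equal. The historical TMA definition is not given. Section 7.2.1 admits TMA without microangiopathy, and the trial tests on a schedule, so observed TMA could rise. For severe TMA, section 7.2.2 requires dialysis or intervention and does not list death, but adds CNS dysfunction and long admission, so its net effect is also open.

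**Efficacy is secondary.** This is a pilot whose primary aims are safety and feasibility, and no formal claim of prevention is defined. That limits the stakes.

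**Conclusion.** The concern holds in a limited form. The benchmarks are unvalidated rates from 22 patients, selected by criteria that owe something to the centre's own cases and very probably measured on a series that includes them. Other things equal they are likely inflated. The size of the inflation cannot be obtained from the documents, and the net direction of all differences between the historical and trial cohorts is not established.

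The consequence depends on the test. Against a fixed 28% for severe TMA, an untreated rate of 20% raises the chance of a false success from 2.0% to 11.5%, and 15% raises it to 28.0%. With Fisher's test against 7/22 for all TMA, the corresponding chances are 3.3% and 10.6%. These figures rest on assumed untreated rates, N=24 and no drug effect. The primary safety and feasibility endpoints are unaffected. The changes should be made, because they are cheap and bear directly on what the trial can say about prevention.

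**What to change.** In sections 8.1, 8.2.1 and 8.4.3:

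1. State which cases, over which dates, informed the criteria, and report 7/22 and 6/22 with their exact 95% intervals.
2. Compare by a named two-sample method that carries the uncertainty of the 22 controls, not against a fixed rate, and restate power on that basis.
3. Recount historical TMA and severe TMA within 6 months of transplant, using the section 7.2 definitions where records allow.
4. Pre-specify a sensitivity table at untreated rates such as 15%, 20% and 25%. If a prevention finding does not hold there, describe it as dependent on the benchmark. By a one-sample exact test at one-sided 2.5%, 0-1 of 24 passes at 25% (p=0.009), but only 0 of 24 passes at 20% (p=0.005) or 15% (p=0.020). A rule barring any claim unless it held at 10% should not be used: even 0 of 24 gives 0.9^24 = 0.080.
5. Optionally, apply the frozen criteria to transplants outside the derivation period and show the rate descriptively. At 22/3.75 years, about 6 high-risk patients per year, this is too few to validate the benchmark.

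The cost is a small chart review and some SAP wording. Enrolment, treatment and the primary endpoints do not change. The drawback is that the apparent benefit may look smaller or less certain.

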1.4 Correlative Studies

Biomarkers indicative of endothelial damage and TMA activity will be drawn to assess subclinical TMA activity as well as risk for subsequent development of TMA while on defibrotide. These include plasma free hemoglobin (UCSF clinical lab), suppression of tumorigenicity (ST2, Viracor), angiotensin 2 (Ang2, Myriad), and plasminogen activator inhibitor – 1 (PAI-1, Quest). Study labs will be assessed at 4 time points prior to Day +21, and at diagnosis of TMA.

Hypothesis:

1. The incidence of TMA will correlate with increases in one or more of these biomarkers over baseline at any time post-HSCT.
2. The severity of TMA will correlate with a maximum increase in one or more of these biomarkers.

This will provide a predictive basis for future patients who may require preemptive treatment of early / preclinical TMA.

2 Objectives of the Study

2.1 Primary

- To determine the safety and feasibility of administering prophylactic Defibrotide (provided by Jazz Pharmaceuticals) to a pilot population of patients at clinical high-risk for the development of severe TMA following HSCT. Safety to be determined with regard to bleeding risk and risk of hypersensitivity reaction. Feasibility to be determined with regard to administration concurrently with chemotherapy and supportive medications before, during, and after stem cell infusion

2.2 Secondary

- To determine if administration of prophylactic Defibrotide will prevent the development of TMA in clinically high-risk patients compared to historic controls.
 - Incidence of TMA in the first 6 months post-HSCT will be compared to incidence in a similar cohort of historical controls.
 - Incidence of severe TMA as defined by any TMA with the following complications:
 - Renal dysfunction requiring dialysis
 - Pleural or pericardial effusion requiring any medical or surgical intervention
 - CNS dysfunction including seizure, PRES
 - Death

